Pharmacokinetics																																		
Serum PK samples for dupilumab concentration p		X	X	X	X	X	X	X	X	X	X	X	X	X	X	X	X	X	X	X	X	X	X	X	X	X	X	X	X	X	X	X		
Anti-dupilumab antibody p		X						X						X														X			X			
Biomarkers																																		
FeNO post-bronchodilator		X		X	X	X	X	X	X	X	X	X	X	X	X	X	X	X	X	X	X	X	X	X	X	X	X	X	X			X		
PARC		X																										X			X			
Eotaxin-3		X		X	X	X	X	X	X	X	X	X	X	X	X	X	X	X	X	X	X	X	X	X	X	X	X	X	X			X		

	Screening	Randomization/ Baseline																																	
VISIT	1	2 a,b	3	4	5	6	7	8	9	10	11	12	13	14	15	16 c	17	18	19																
WEEK	W-4 to W-1	0	2	4	6	8	10	12	14	16	18	20	22	24	26	28	30	32	34	36	38	40	42	44	46	48	50	52 (EOT)	56	60	64 (EOS)				
Total IgE		X						X																			X						X		
Fibrinogen		X										X															X							X	
Induced/spontaneous sputum (optional) m		X										X															X								
Whole blood RNA (optional)		X										X															X								
DNA (optional)		X q																																	
Serum/plasma for archival samples (optional)		X		X				X				X							X								X								
Efficacy																																			
COPD exacerbation reporting by the Investigator		X	X	X		X		X		X		X		X		X		X		X		X		X		X	X	X		X	X	X			
Spirometry (pre-BD) n,o	X	X	X	X		X		X		X		X		X		X		X		X		X		X		X	X	X		X	X	X			
Spirometry (post-BD) n,o	X	X	X	X		X		X		X		X		X		X		X		X		X		X		X		X		X				X	
EXACT g	Every day (diary) from screening to week 52																																		
SGRQ g		X		X				X						X					X								X								X
EQ-5D-5L g		X																																	
Health care utilization f		X		X		X		X		X		X		X		X		X		X		X		X		X	X	X		X					X
At-home spirometry (FEV1) Optional assessments (US/Canada only) f	BID	BID						BID																											

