2 STATISTICAL AND ANALYTICAL PROCEDURES

2.1 ANALYSIS ENDPOINTS

2.1.1 Demographic and baseline characteristics

The baseline value of efficacy parameters is defined as the last available value up to randomization but prior to the first dose of study medication unless otherwise specified. The baseline value of the other parameters is defined as the last available value prior to the first dose of investigational medicinal product (IMP) if the patient is treated, or the last available value up to randomization if the patient is not exposed to IMP.

The calculation of the baseline for daily ed diary questionnaire scores will be specified in [Section 2.1.3.2.2.1](#).

All baseline safety and efficacy parameters (apart from those listed below) will be presented along with the on-treatment summary statistics in the safety and efficacy sections ([Section 2.4.5](#) and [Section 2.4.4](#)).

Demographic characteristics

Demographic variables are

- Gender (Male, Female),
- Race (Caucasian/White, Black/of African descent, Asian/Oriental, American Indian or Alaska Native, Native Hawaiian or other Pacific Island, Unknown)
- Ethnicity (Hispanic or Latino, Not Hispanic or Latino, Unknown)
- Age in years (quantitative and qualitative variable: 40-64, 65-74, 75-80 years)
- Region (Asia: Japan, China, South Korea; Latin America: Argentina, Chile and Mexico; East Europe: Russia, Ukraine, Turkey, Hungary, Poland, Czech Republic, Romania, Bulgaria, Slovakia; Western Countries: Finland, Denmark, Spain, Israel, Sweden, Germany, Italy, Canada, USA)
- Territory (Canada and USA: Canada and USA; European Union: Hungary, Poland, Czech Republic, Romania, Bulgaria, Slovakia, Spain, Sweden, Germany, Italy, Finland, Denmark; Rest of World: Israel, Argentina, Chile, Japan, China, South Korea, Mexico, Russia, Ukraine, Turkey)
- Weight in kg (quantitative and qualitative variable : <50, 50-<100 and ≥ 100 kg)
- BMI in kg/m^2 (quantitative and qualitative variable: <30, ≥ 30 kg/m^2)

Medical or surgical history

Medical (or surgical) history includes all the relevant medical (or surgical) history during the lifetime of the patient.

This information will be coded using the version of Medical Dictionary for Regulatory Activities (MedDRA) currently in effect at Sanofi at the time of database lock.

Comorbidity will be summarized separately. The following comorbid diseases will be summarized from eCRF pages which were filled in by investigators based on patient reporting.

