than 4 days of data are available in the 7-day window, the EXACT score cannot be calculated and will be considered as missing. For the exacerbation analysis, the baseline would be reset during the study. Additional information related to computing scores and frequency, severity, and duration of events can be found in the user manual (6).

The Evaluating Respiratory Symptoms (E-RS) in COPD (E-RS: COPD) scale is a part of the EXACT tool. It is a derivative instrument used to measure the effect of treatment on the severity of respiratory symptoms in stable COPD. The E-RS utilizes the 11 respiratory symptom items contained in the 14-item EXACT.

The daily RS-Total score is computed by taking the sum of the 11 items comprising the instrument. It has a range of 0 to 40, with higher values indicating more severe respiratory symptoms.

The same summation procedure is used to derive the three daily domain scores:

- RS-Breathlessness (sum of items 7, 8, 9, 10, and 11; score range 0–17)
- RS-Cough and Sputum (sum of items 2, 3, 4; score range 0–11)
- RS-Chest Symptoms (sum of items 1, 5, 6; score range 0–12)

Like for EXACT, the baseline RS score as well as the post-baseline weekly domain and total scores are calculated as the mean within-patient score over the prior 7 days, with data present for a minimum of 4 of the 7 days. If fewer than 4 days of data are available in the 7-day window, the RS scores cannot be calculated and will be considered as missing.

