2.4.4.2 Analyses of key secondary efficacy endpoints

2.4.4.2.1 Analysis of the change from baseline in pre-bronchodilator(pre-BD) FEV1 at Week 12 for dupilumab versus placebo

The change from baseline in pre-bronchodilator FEV1 at Week 12 will be analyzed using mixed-effect model with repeated measures (MMRM). The analysis will be performed in the full ITT population and also in the baseline FENO ≥ 20 ppb subgroup. The model will include change from baseline in FEV1 values up to Week 12 as response variables, and factors for treatment group, age, sex, height, region (pooled country), ICS dose at baseline (high dose ICS [yes/no]), smoking status at screening (current smokers or not), visit, treatment-by-visit interaction, baseline pre-bronchodilator FEV1, and FEV1 baseline-by-visit interaction as covariates. An unstructured correlation matrix will be used to model the within-patient errors. Parameters will be estimated using restricted maximum likelihood method using the Newton-Raphson algorithm. The least square (LS) mean of the change in pre-bronchodilator FEV1 of each treatment group, difference in the LS mean changes between the dupilumab group and placebo, the corresponding 95% CI of the differences and p-values will be provided. For patients who discontinued the study treatment, off-treatment FEV1 values will be included in the analysis.

Subgroup analyses

To assess the consistency treatment effects across the subgroup levels, subgroup analyses will be conducted for the change from baseline in pre-BD FEV1 at Week 12 with the same set of subgroups as defined for the annualized rate of moderate or severe AECOPD events in [Section 2.4.4.1](#).

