For the efficacy assessment, the reference date for the derivation of relative days of events or findings will be the randomization day. If a patient receives IMP prior to the randomization by mistake, the reference date of efficacy assessment will be the date of the first IMP administration for that patient. For the primary analyses, all available values of scheduled measurements will be assigned to the appropriate visit window according to [Table 7](#). In the event of multiple measurements of the same test in the same window, the one closest to the targeted visit date will be used for the by-visit summary. If they are at the same distance to the target day, the latest one will be used.

Table 7 – Time window for efficacy variables

Visit	Target Day	Time windows for		
		Pre-bronchodilator Spirometry	Post-bronchodilator Spirometry	SGRQ
Visit 1 (Week -4±1)	-28±7	<-14	<-14	
Visit 2 (Week 0)	1	-14-1	-14-1	1
Visit 3 (Week 2)	15	1+-21	1+-21	
Visit 4 (Week 4)	29	22-42	22-42	1+-56
Visit 5 (Week 8)	57	43-70	43-70	
Visit 6 (Week 12)	85	71-98	71-126	57-126
Visit 7 (Week 16)	113	99-126		
Visit 8 (Week 20)	141	127-154		
Visit 9 (Week 24)	169	155-182	127-210	127-210
Visit 10 (Week 28)	197	183-224		
Visit 11 (Week 32)	225			
Visit 12 (Week 36)	253	225-280	211-308	211-308

Visit	Target Day	Time windows for		
		Pre-bronchodilator Spirometry	Post-bronchodilator Spirometry	SGRQ
Visit 13 (Week 40)	281			
Visit 14 (Week 44)	309	281-322		
Visit 15 (Week 48)	337	323-350		
Visit 16 (Week 52)	365	351-378	309-406	309-406
Visit 17 (Week 56)	393	379-406		
Visit 18 (Week 60)	421	407-434		
Visit 19 (Week 64)	449	>434	>406	>406

1-: up to randomization and before 1st dose date/time; 1+: after randomization or 1st dose date/time

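### The FEV1 models adjust for one pre-treatment FEV1 although a second is collected at Visit 1; adding it is a near-free precision gain, mainly for the two FeNO-subgroup tests

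*SAP*

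**What the plan says.** SAP section 2.4.4.2.1 fits a mixed model for repeated measures to the change in pre-bronchodilator FEV1, in the full ITT population and in patients with baseline FeNO of at least 20 ppb. Its covariates start with "factors for treatment group, age, sex, height, region (pooled country), ICS dose at baseline", add smoking status, and end with "visit, treatment-by-visit interaction, baseline pre-bronchodilator FEV1, and FEV1 baseline-by-visit interaction as covariates". Section 2.4.4.2.2 carries the model to Week 52. The Appendix J imputation and ANCOVA for Week 12 also use one baseline FEV1.

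SAP section 2.1.1 says what that value is: it is "defined as the last available value up to randomization but prior to the first dose of study medication". That is Visit 2 in the ordinary case, and Visit 1 only if Visit 2 is missing.

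The Protocol's schedule of activities (section 1.3.1) marks pre-bronchodilator spirometry at both Visit 1 and Visit 2. Its spirometry footnote sets one washout rule for all visits. SAP Table 7 (section 2.5.4), in the column "Pre-bronchodilator Spirometry", gives Visit 1 a window of its own (before Day -14), apart from Visit 2 (Day -14 to Day 1).

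Four FEV1 tests stand in the fixed sequence of SAP section 2.4.4.3 at two-sided 0.049: Week 12 and Week 52 in the full population (steps 2 and 3), then both in the FeNO subgroup (steps 4 and 5).

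**The concern.** A single FEV1 reading mixes the patient's underlying level with day-to-day noise. A second reading about four weeks earlier, under the same washout, helps separate the two and so predicts later FEV1 better than one reading alone. Because it precedes randomization, adjusting for it leaves the estimand unchanged. The data are already in hand.

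What is at stake is precision on tests that gate others. If step 4 or 5 fails, the SGRQ change, the SGRQ responder proportion, E-RS and the subgroup exacerbation rate cannot be formally tested. Neither document states the subgroup's expected size or its power.

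**Working it through.** **Inputs from the documents.** 462 patients per arm, effect 0.1 L, SD 0.35 L, 5% missing and two-sided alpha 0.049 (Protocol section 9.2). Screening lasts 4 weeks, give or take 1 (Protocol section 4.1). The covariance is unstructured and no correlation is given, so every correlation below is an assumption.

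**1. The plan's own figure.** n per arm = 462 × 0.95 = 438.9. Standard error = 0.35 × √(2/438.9) = 0.0236 L. Power = Φ(0.1/0.0236 − 1.969) = 98.8%. The Protocol's 99% reproduces.

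**2. Formula for the gain.** Let r12 be the correlation of Visit 1 with Visit 2, and r2W and r1W the correlations of Visits 2 and 1 with the endpoint visit, all after the other covariates. With complete data, the unstructured model at the target visit behaves like an ANCOVA:

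- One baseline: residual variance is proportional to 1 − r2W².
- Two baselines: it is proportional to 1 − R², with R² = (r2W² + r1W² − 2·r2W·r1W·r12)/(1 − r12²).
- Standard-error ratio = √[(1 − R²)/(1 − r2W²)]. If all three correlations equal r, this is √(1 + 2r)/(1 + r).

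**3. Equal correlations.** At r = 0.8: √2.6/1.8 = 0.896, a 10.4% reduction. At r = 0.5 it is 5.7%, and at r = 0.95 it is 12.7%. A simulation (878 patients, 4,000 runs) gave 4.9%, 9.6% and 13.1% at r = 0.5, 0.8 and 0.95.

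**4. Visits 1 and 2 closer to each other than to the endpoint.** With r12 = 0.9 and r2W = r1W = 0.8: R² = (1.28 − 1.152)/0.19 = 0.674, ratio = √(0.326/0.36) = 0.952, a 4.8% reduction. With r1W = 0.78 instead it is 2.7%. With r12 = 0.95 and both others 0.8 it is 2.3%.

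**5. Correlation decaying with time.** Take correlation = reliability × c^(weeks/52), where c is the correlation of true FEV1 over one year and the two baseline visits are 4 weeks apart.

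| Reliability | c | Week 12 | Week 52 |
|---|---|---|---|
| 0.80 | 0.95 | 9.5% | 7.7% |
| 0.90 | 0.95 | 10.1% | 7.1% |
| 0.90 | 0.90 | 8.5% | 4.7% |
| 0.95 | 0.70 | 2.7% | 0.6% |

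Over reliability 0.80-0.95 and c from 0.95 down to 0.70, the reduction is 2.7-10.1% at Week 12 and 0.6-7.7% at Week 52.

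**6. What it buys.** Full population, Week 12: a 6% reduction moves power from 98.8% to 99.4%. For the FeNO subgroup, assume 25-50% of patients and keep 0.1 L, 0.35 L and 5% missing. Then n per arm is 110-219 and power = Φ(0.1/(0.35·√(2/n)·s) − 1.969), where s is the standard-error ratio:

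| Reduction | 25% share | 50% share | Equivalent extra patients |
|---|---|---|---|
| none | 56% | 85% | none |
| 3% | 58% | 87% | 1/0.97² − 1 = 6% |
| 6% | 61% | 89% | 1/0.94² − 1 = 13% |

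**The case against.** The planned model is valid, its single baseline is explicitly defined, and the Protocol specifies one baseline too (section 9.4.1, Table 9). There is no contradiction, bias or error-rate problem, and a reader who infers one goes beyond the documents. That stands.

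A reader might also infer an unconditional loss of 6-13%. The documents do not support it, since that range needs equal correlations and they state none. Two features of the design point lower. Age, sex and height already absorb part of the between-patient variance. In a structured model with within-patient variance 0.35²/2, of which 25-50% is slow drift, a residual between-patient SD of 0.25-0.30 L gives only about 3-6%. Patients are also selected at screening on post-bronchodilator FEV1. In a simulation of selection on the Visit 1 value (assumed percent-predicted SD 12-20, visit noise 5-7), the equal-correlation gain fell from 9.6-12.6% to 7.0-10.1%.

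Nor do all four tests gain alike. In the full population at Week 12 there is almost no power left to win, and the documents give no Week 52 power figure.

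The subgroup starting power may be understated. If 0.35 L is a change-score SD and the between-patient SD is 0.4-0.6 L, the baseline-adjusted SD without drift is 0.325-0.337 L. Starting power at a 50% share is then 87-90%, not 85%. This shifts the starting point but leaves the gain.

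Finally, it would be too strong to say that Visit 1 is discarded, because it serves as the fallback baseline. A similar gain might be inferred for E-RS, whose baseline uses only seven diary days, but nothing in the documents sizes it and none is claimed here.

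**Conclusion.** The point holds as a missed efficiency gain. Facts and direction are firm: a second eligible value exists, the models leave it out as a covariate, and including it cannot harm large-sample precision. The size is uncertain. The standard error is about 6-13% lower if correlations are equal at 0.5-0.95, or about 3-10% lower at Week 12 and 1-8% lower at Week 52 if correlation decays with time. The material benefit is in steps 4 and 5 of the hierarchy, where a 3-6% reduction adds about 2 to 5 points of power. That figure rests on an assumed 25-50% subgroup share and on carrying 0.1 L and 0.35 L over from the full population.

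**What to change.** - Add Visit 1 pre-bronchodilator FEV1 and its interaction with visit to the Week 12 and Week 52 models, in the full population and in the FeNO subgroup.
- Add Visit 1 FEV1 as a covariate in the Appendix J imputation and ANCOVA.
- Identify Visit 1 by its nominal visit. If it is missing, substitute the Visit 2 value.
- Keep Visit 2 as the baseline for the change score.
- Specify this before unblinding, and record the departure from the Protocol's covariate list in SAP section 1.5.

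The cost is SAP wording and one covariate, about one degree of freedom per visit. No new data are needed and the estimand does not change.

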2.4.4.3 Multiplicity issues

The multiplicity procedure is proposed to control the overall type-I error rate for testing the primary and selected secondary endpoints listed below. The overall alpha is 0.05.

A non-binding futility interim analysis (IA) is planned in this study (details are provided in [Section 3](#)), and an administrative penalty of 0.001 will be taken from the significance level used at final analysis and thus two-sided 0.049 will be used. No further multiplicity adjustment will be performed for the IA.

At the final analysis, the comparisons with placebo will be tested based on the hierarchical order below at 2-sided $\alpha=0.049$.

1) Primary efficacy endpoints:

- Annualized rate of moderate or severe COPD exacerbations over the 52-week treatment period compared to placebo.

2) Secondary/exploratory efficacy endpoints:

- Change in pre-bronchodilator FEV1 from baseline to Week 12 compared to placebo
- Change in pre-bronchodilator FEV1 from baseline to Week 52 compared to placebo
- Change in pre-bronchodilator FEV1 from baseline to Week 12 compared to placebo in the subgroup of patients with baseline FENO ≥ 20 ppb
- Change in pre-bronchodilator FEV1 from baseline to Week 52 compared to placebo in the subgroup of patients with baseline FENO ≥ 20 ppb
- Change from baseline to Week 52 in SGRQ total score compared to placebo
- Proportion of patients with SGRQ improvement ≥ 4 points at Week 52 compared to placebo
- Change in E-RS COPD scores from baseline to Week 52 compared to placebo
- Annualized rate of moderate or severe COPD exacerbation compared to placebo over the 52-week treatment period in the subgroup of patients with baseline FENO ≥ 20 ppb

The study is considered positive when the primary endpoint achieves statistical significance.

2.4.4.4 Additional efficacy analyses

2.4.4.4.1 Comparisons for other secondary efficacy endpoints

- Change in pre-bronchodilator FEV1 from baseline to Weeks other than 12 and 52
- Change in post-bronchodilator FEV1, forced expiratory flow (FEF) 25-75%, FEV1/FVC from baseline to Weeks up to Week 52
- Time to first moderate or severe COPD exacerbation compared to placebo during the 52-week treatment period
- Annualized rate of severe COPD exacerbations over the 52-week treatment period

2.4.4.4.2 Analyses of other efficacy endpoints for dupilumab versus placebo up to Week 52

Change from baseline in continuous endpoint (pre-bronchodilator FEV1, post-bronchodilator FEV1, FEF25-75%, SGRQ total scores) at all time-points will be analyzed in a similar way as change from baseline in pre-bronchodilator FEV1 at Week 52. Age, sex and height will be included as covariates only in the models for spirometry parameters. Descriptive statistics including number of patients, mean, standard error, and least squares (LS) means will be provided for all visits. In addition, difference in LS means and the corresponding 95% confidence intervals (CI) will be provided along with the p-values.

Proportion type efficacy endpoints (SGRQ improvement from baseline ≥ 4 points) during the treatment period will be analyzed in a similar way as proportion of patients with SGRQ improvement ≥ 4 points at Week 52, except that the response variable will be the responder status at the corresponding visit instead of at Week 52. Odds ratio of being a responder comparing dupilumab to placebo will be provided along with the corresponding 95% CI and p-value at each visit. Descriptive statistics including number and percentage of responders will also be provided.

2.4.4.4.3 Analyses of time to first moderate or severe COPD exacerbation compared to placebo during the 52-week treatment period

The time to first moderate or severe COPD exacerbation will be analyzed using a Cox regression model. The model will include the time to the first event as the dependent variable, and treatment group, region (pooled country), ICS dose at baseline (high dose ICS [yes/no]), smoking status at screening (current smokers or not), baseline disease severity (as % predicted post-bronchodilator FEV1), and number of moderate or severe COPD exacerbation events within one year prior to the study (≤ 2 , 3, or ≥ 4) as covariates. Hazard ratio and corresponding 95% CI and p values will be estimated for dupilumab versus placebo. The

Kaplan–Meier method will be used to derive the probabilities that a patient would experience an event up to specific timepoints for each treatment group. Kaplan–Meier curves will be generated; point probabilities will be calculated. Interval estimates will be calculated using 95% point wise confidence intervals.

2.4.4.4 Analyses of annualized rate of severe COPD exacerbations over the 52-week treatment period

The annualized event rate of severe COPD exacerbations will be analyzed in the same way as the primary analysis for the annualized rate of moderate or severe COPD exacerbation events. The estimated event rate for each treatment group and its two–sided 95% confidence intervals will be provided. The event rate ratio of dupilumab against placebo, two–sided 95% confidence intervals of the rate ratio and the corresponding p–value will also be provided.

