#### Type of participant and disease characteristics

I 02. Participants with a physician diagnosis of COPD who meet the following criteria:

- Current or former smokers with a smoking history of  $\geq 10$  pack-years
- Moderate to severe COPD (post-bronchodilator  $FEV_1/FVC \leq 70\%$  and post-bronchodilator  $FEV_1$  % predicted  $>30\%$  and  $\leq 70\%$ ).
- Medical Research Council (MRC) Dyspnea Scale grade  $\geq 2$ .
- Patient-reported history of signs and symptoms of chronic bronchitis (chronic productive cough) for 3 months in the year up to screening in the absence of other known causes of chronic cough.
- Documented history of high exacerbation risk defined as exacerbation history of  $\geq 2$  moderate\* or  $\geq 1$  severe\*\* within the year prior to inclusion.

\*Moderate exacerbations are recorded by the investigator and defined as AECOPD that require either systemic corticosteroids (intramuscular (IM), intravenous, or oral) and/or antibiotics. One of the two required moderate exacerbations has to require the use of systemic corticosteroids.

\*\*Severe exacerbations are recorded by the investigator and defined as AECOPD requiring hospitalization / emergency room / urgent care visit.

- Background triple therapy (ICS+ LABA+ LAMA) for 3 months prior to randomization with a stable dose of medication for  $\geq 1$  month prior to Visit 1: (Double therapy: LABA + LAMA allowed if ICS is contraindicated)

I 03. Evidence of Type 2 inflammation: Patients with blood eosinophils  $\geq 300$  cells/microliter at Visit 1 (Screening).

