1.3 DETERMINATION OF SAMPLE SIZE

The sample size of the study is determined based on power calculations for the primary endpoint of annualized rate of acute moderate or severe COPD exacerbations over the 52-week treatment period. Assuming the number of exacerbations follows a negative binomial distribution with a dispersion parameter of 1, a placebo annualized rate of exacerbations of 1.5, an average treatment duration of 0.95 year (to account for an average of 5% of the planned treatment period with missing data), and a randomization ratio of 1:1 to the two treatment arms, with 924 randomized patients (462 for each treatment arm), the study will have 90% power to detect a 25% relative risk reduction (ie, annualized rate of 1.125 for the dupilumab group) in the annualized rate of moderate or severe COPD exacerbations at the 2-tailed significance level of $\alpha=0.049$ (an administrative penalty of 0.001 will be taken from the significance level used at final analysis due to a planned interim analysis; details are provided in [Section 3](#)).

Patients will be randomized using a 1:1 randomization ratio to dupilumab 300 mg q2w or placebo. Randomization will be stratified by country and by ICS dose (high dose ICS [yes/no]) at baseline.

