For each of the above methods, a negative binomial model will be fitted using each of the complete datasets composed of observed and imputed data, including the total number of observed and imputed events during the 52 weeks as the response variable, with the treatment group, region (pooled country), ICS dose at baseline (high dose ICS [yes/no]), smoking status at screening (current smokers or not), baseline disease severity (as % predicted post-bronchodilator FEV1), and number of moderate or severe COPD exacerbation events within one year prior to the study (≤ 2 , 3, or ≥ 4) as covariates. Log transformed observation duration will be the offset variable for patients who complete the 52-Week treatment/study period, and log transformed 52 weeks will be the offset variable for patients who discontinue the study before Visit 16 (Week 52). SAS MIANALYZE procedure will be used to generate statistical

inferences by combining results from the analysis with each dataset using Rubin's formula.

More details of the imputation and analyses methods are provided in Appendix J:

Subgroup analyses

To assess the consistency in treatment effects across different subgroup levels, subgroup analyses will be conducted for the primary efficacy endpoint with respect to:

- Age group (<65, ≥65 years)
- Gender (Male, Female)
- Region
- Territory
- Race (Caucasian/White, Black/of African descent, Asian/Oriental, Others)
- Ethnicity (Hispanic or Latino, Not Hispanic or Latino)
- Baseline weight (<70, ≥70- < 90, ≥ 90 kg; <60, ≥ 60 kg)
- Baseline BMI (<25, ≥25- <30, ≥30 kg/m²)
- ICS high dose level at baseline (Yes, No)
- Smoking status at screening (current smokers, former smokers)
- Number of moderate-or-severe COPD exacerbation events within one year prior to V1 (≤2, 3, or ≥4)
- Number of severe COPD exacerbation events within one year prior to V1 (0, 1, ≥ 2)
- Baseline predicted post-bronchodilator FEV1% (<50%, ≥50%)
- Baseline pre-bronchodilator FEV1 (< median, ≥ median)
- Baseline FEV1 reversibility (<12%, ≥ 12%; < median, ≥ median)
- Baseline fractional exhaled nitric oxide (FeNO) (<20, ≥ 20 ppb)
- Baseline eotaxin-3 (< median, ≥ median)
- Baseline IgE (< 100 , ≥ 100 IU/ml)
- Baseline PARC (< median, ≥ median)
- Baseline Fibrinogen (< 350, ≥ 350 mg/dL)
- Baseline mMRC (< median, ≥median)
- Maximum eosinophils counts during screening (≥ 0.3-<0.5, ≥0.5 Giga/L)

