2.4.4.5 Analyses of exploratory efficacy endpoints

2.4.4.5.1 Analyses of other continuous endpoints

For post-bronchodilator FEV1, the rate of change in FEV1 (termed as FEV1 slope) will be compared between dupilumab against placebo. Repeated post-bronchodilator FEV1 after Week 4 and after Week 8 up to Week 52 will be analyzed correspondingly using linear mixed-effects model with treatment, age, sex, height, region (pooled country), ICS dose at baseline (high dose ICS [yes/no]), smoking status at screening (current smokers or not), time since randomization, and treatment-by-time interaction and baseline post-bronchodilator FEV1 as covariates. Intercept and time since randomization are random effects. Individual post-BD FEV1 slope will be calculated as the slope of a linear regression model with the post-BD FEV1 (L) at each visit as the response variable and the time since randomization as the independent variable. Descriptive statistics including number of patients, mean, standard error of the individual post BD FEV1 slopes will be provided. Estimated from the linear mixed-effects model, least squares (LS) means, difference in LS means and the corresponding 95% confidence intervals (CI) will also be provided.

Change from baseline in FVC (percent predicted and absolute change in ml), weekly E-RS symptom scores at all time-points will be analyzed in a similar way as change from baseline in pre-bronchodilator FEV1 at Week 52. Age, sex and height will be included as covariates only in the models for spirometry parameters. Descriptive statistics including number of patients, mean, standard error, and least squares (LS) means will be provided. In addition, difference in LS means and the corresponding 95% confidence intervals (CI) will be provided.

2.4.4.5.2 Analyses of time to first severe COPD exacerbation compared to placebo during the 52-week treatment period

The time to first severe COPD exacerbation will be analyzed using the same approach as that for the analyses of time to first moderate or severe COPD

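### The severe-exacerbation rate model adjusts only for the combined prior event count; adding the prior severe count, already collected and classed, would be a small, low-cost gain.

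*SAP*

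**What the plan says.** - **Severe rate** (SAP 2.4.4.4, an other secondary endpoint): "The annualized event rate of severe COPD exacerbations will be analyzed in the same way as the primary analysis for the annualized rate". The reference is to the model for the combined endpoint. Protocol Table 9 says the same.
- **Covariates carried over** (SAP 2.4.4.1): treatment, region, ICS dose, smoking status, % predicted post-bronchodilator FEV1, and the combined count of moderate or severe events in the prior year, classed ≤2, 3 or ≥4.
- **Time to first severe event** (SAP 2.4.4.5.2, exploratory): "The time to first severe COPD exacerbation will be analyzed using the same approach as that for the analyses". The reference is to the Cox model for the combined endpoint, which has the same covariates.
- **Entry** (Protocol 5.1, I 02): "Documented history of high exacerbation risk defined as exacerbation history of" at least 2 moderate or at least 1 severe event in the prior year.
- **Prior severe count**: SAP 2.1.1 lists it as a baseline characteristic. SAP 2.4.4.1 lists "Number of severe COPD exacerbation events within one year prior to V1" as a subgroup factor, classed 0, 1, ≥2. That subgroup list serves the primary endpoint and Week 12 FEV1. The additional subgroup analysis that reaches the severe rate names smoking status only.

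**The concern.** The history covariate was built for the combined endpoint and reaches the severe endpoint by cross-reference. For severe events it can order patients poorly: one severe and no moderate event falls in the lowest class, while four moderate and no severe events fall in the highest. The class ≤2 holds two moderate events; one severe; one severe plus one moderate; and two severe.

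If prior severe events predict later ones beyond the total count and FEV1, two things follow. The interval for the severe rate ratio is slightly wider than it need be, and a chance imbalance in prior severe events is corrected only in part. Randomisation does not balance exacerbation history; the SAP stratifies by country and ICS dose.

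**Working it through.** **1. The plan's own figure.** SAP 1.3 says "the study will have 90% power to detect a 25% relative risk reduction", with "a placebo annualized rate of exacerbations of 1.5", counts that "follows a negative binomial distribution with a dispersion parameter of 1", 0.95 year of follow-up, 462 per arm and two-sided α = 0.049.

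Var(log RR) = (1/n)[1/(t·r0) + k + 1/(t·r1) + k] = (1/462)[1/1.425 + 1 + 1/1.06875 + 1] = 0.007873, so SE = 0.0887. Power = Φ(0.2877/0.0887 − 1.9686) = 0.899, against 90% stated. The variance formula is therefore suitable. The documents give no rate, dispersion or power for severe events.

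**2. One worked case for the severe rate.** Assumed, not in the documents: placebo severe rate 0.2 per year, treatment rate ratio 0.7, 35% with a prior severe event, residual rate ratio 2 for them, dispersion 1 after adjustment, α = 0.05.

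- Mean counts: 0.95 × 0.2 = 0.19 on placebo and 0.133 on dupilumab.
- Dispersion if the factor is left out: 2 × (0.65 + 0.35 × 4)/1.35² − 1 = 1.25.
- Left out: (1/462)(1/0.19 + 1/0.133 + 2 × 1.25) = 0.03308; SE 0.1819.
- Included: placebo means are 0.1407 (no prior severe) and 0.2815 (prior severe). Information = 300.3/(1/0.1407 + 1/0.0985 + 2) + 161.7/(1/0.2815 + 1/0.1970 + 2) = 15.60 + 15.21 = 30.81. Variance 0.03246; SE 0.1802.
- Variance falls 1.9%; power goes from 0.500 to 0.508.

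Over rates 0.1–0.3, prevalence 20–50% and dispersion 1–2, the same formula gives 0% at residual ratio 1, 0.3–1.1% at 1.5, 0.8–3.2% at 2 and 1.8–8.3% at 3. The gain is small because the term 1/(t·r) dominates at a low rate, and the covariate acts only on the dispersion term.

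**3. Against the model the SAP actually has.** That model already contains the total count. Assumed joint shares (prior severe 0 / 1 / ≥2; 39% with any):

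| Total count | 0 | 1 | ≥2 |
|---|---|---|---|
| ≤2 | 0.40 | 0.20 | 0.02 |
| 3 | 0.14 | 0.07 | 0.02 |
| ≥4 | 0.07 | 0.05 | 0.03 |

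Cell means are proportional to the product of a total-count effect and a prior-severe effect. Each adjustment class g contributes n·w_g/(1/μ0 + 1/μ1 + 2k_g), with k_g = (1 + k)·E[μ²]/E[μ]² − 1 within the class. Severe rate 0.1–0.2, k = 1–2. Change in variance relative to the SAP model:

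| Total-count effects | Prior-severe effects | Add | Replace |
|---|---|---|---|
| 1/1.5/2.5 | 1/1/1 | 0% | +1.2 to +2.7% |
| 1/1.5/2.5 | 1/1.5/2 | −0.6 to −1.4% | +0.6 to +1.5% |
| 1/1.5/2.5 | 1/2/3 | −1.7 to −3.5% | −0.3 to −0.5% |
| 1/1.3/1.8 | 1/1.5/2 | −0.6 to −1.2% | −0.1 to −0.2% |
| 1/1.3/1.8 | 1/2/3 | −1.5 to −3.3% | −1.0 to −2.1% |

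Adding helps wherever prior severe events are prognostic and costs nothing in variance where they are not. Replacing can go either way.

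**4. Simulation.** 924 patients, histories generated by the two entry routes, 400–500 trials per scenario; models with the SAP history classes and FEV1, with and without prior severe 0/1/≥2 (region, ICS dose and smoking left out).

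- Negative binomial: variance falls 0.9–1.9% at residual ratio 2 and 2.0–5.0% at 3, the top value at a placebo rate of 0.3.
- Cox: the SE does not fall (0.1875 to 0.1880 at residual ratio 3); the log hazard ratio moves from −0.305 to −0.313.
- Under no treatment effect, rejection was 0.050 with and without the term, in both models.

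**5. Chance imbalance.** With 35% prevalence, the arm difference has SD √(2 × 0.35 × 0.65/462) = 3.1 points. At residual ratio 2, a 2-SD imbalance (6.3 points) shifts the unadjusted rate ratio by 1.381/1.319 = 1.05, about 5%.

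**The case against.** The strongest case for leaving the plan alone has four parts.

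- **Predictive strength is unknown.** That precision is lost at all depends on prior severe events predicting beyond the total count and FEV1, and the documents give no figure. This stands; the gain must be stated as conditional.
- **The history variable is looser than the outcome.** I 02 counts any emergency room or urgent care visit as severe. The SAP's on-study definition needs more than 24 hours of such care, hospitalisation or death, and uses adjudicated events only. This stands, and would weaken the gain.
- **The consequence is slight.** The severe rate is outside the hierarchy in SAP 2.4.4.3, for which "used at final analysis and thus two-sided 0.049 will be used". Time to first severe event is exploratory. This stands.
- **A common covariate set keeps the exacerbation analyses comparable.** This is a fair preference, and adding a term while keeping the rest respects most of it.

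Stronger readings that a reader might infer are not supported:

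- **That the total count is the wrong covariate and should be replaced.** Step 3 shows that replacement can raise the variance, and it discards moderate-event history.
- **That the interval for time to first severe event is also too wide.** The Cox standard error does not shrink; leaving out a prognostic factor only pulls the hazard ratio slightly toward 1.
- **That the severe-rate analysis is biased or invalid.** Simulated type I error was the same either way.
- **That the loss is 1.3–6.8% of variance.** That range arises (severe rate 0.10–0.20, dispersion 2–4) only against a model with no history covariate, which is not the SAP's model.

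**Conclusion.** The point holds as a refinement. The severe-rate model omits a baseline variable that is close to its outcome, already collected and already classed, while its only history covariate mixes the two entry routes in its lowest class.

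The expected gain is modest: roughly 0.5–3.5% lower variance of the log rate ratio (at most about 1.8% of interval width, from 1 − √0.965), if prior severe events carry a residual rate ratio of about 1.5–3 and the severe rate is 0.1–0.2 per year. A rate near 0.3 with a ratio of 3 could give somewhat more; a ratio of 1 gives nothing. The severe rate, dispersion, prevalence and prognostic effects are all assumptions. In the Cox model the benefit is limited to protection against chance imbalance and against attenuation of the hazard ratio. No confirmatory conclusion depends on this.

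**What to change.** Before unblinding, amend the severe-rate subsection of SAP 2.4.4.4 to say that the model also includes the number of severe exacerbations in the year before Visit 1 (0, 1, ≥2), and keep the existing total-count covariate. The same term may be added in SAP 2.4.4.5.2 for the Cox model, with chance imbalance and attenuation given as the reason rather than precision.

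The cost is one clause in each place and two more parameters per model. No new data are needed and the classes already exist. At the assumed rates of 0.1–0.2, about 462 × 0.95 × 0.1 × 1.7 = 75 to 149 severe events would be expected, so two more parameters are affordable. Fixing the term now also avoids a post hoc adjustment should the arms turn out imbalanced.
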